1.0 Objectives

1.1 Specific Aims.

This study will determine the feasibility of offering expanded continuous labor support by trauma- and addiction-trained medical paraprofessionals (i.e. doulas) at no cost to pregnant women receiving care for substance use disorders (SUD). The long-term goal of this transdisciplinary multilevel intervention is ultimately to reduce a major existing behavioral health disparity in the state.

Pregnant women with substance use disorders (SUD) disproportionately have low socio-economic status and co-occurring mental health problems, especially trauma-related disorders.¹⁻⁴ Additionally, women of color experience behavioral health disparities in care and higher rates of poor maternal and infant behavioral and medical health outcomes.⁵⁻¹³ Women with prenatal SUD are consistently under-resourced and are at high risk for homelessness, loss of child custody, incarceration, loss of parental rights, birth defects, stillbirth, infant death, and child abuse and neglect. There is high long-term postpartum morbidity among women with deliveries complicated by alcohol or drugs, including higher rates of mental, viral, and bacterial illness and requiring an increased need in more medical and social services.^{9,14} These women are 38 times more likely than controls to die within 9 years of giving birth.¹⁴ SUD relapse rates during pregnancy are high, often around 50%,^{15,16} with uniquely high risks in this population. Many women with prenatal SUD have extensive trauma histories, and are at increased risk of postpartum PTSD, SUD relapse, postpartum depression, poor mother-infant attachment, and of development or aggravation of PTSD from traumatic birth experiences.^{11,17-21}

Paraprofessional continuous labor support may offer a low-cost method of improving these outcomes.²² “In this proposal, the term “doula” refers to a person trained to provide continuous labor support. A recent Cochrane report found that continuous labor support was associated with less emotionally traumatic birth outcomes (i.e., adverse events that can happen during childbirth that might be emotionally traumatic for a woman giving birth, such as cesarean section, instrumental vaginal birth, or extended labor).²³ Two states, Minnesota and Oregon, in the U.S. already allow Medicaid reimbursement for doula services.²⁴ In New Mexico doulas are not covered by Medicaid. This creates a behavioral health disparity, by which women with high economic status predominantly have access to these supportive services. This pilot study is intended to explore the feasibility of offering access to trauma and SUD trained doulas at no cost to women in the XXX program at XXX.

This cross-campus multi-disciplinary collaboration, is in partnership with Young Women United (a research and policy organization in NM) and doulas of the UNM Birth Companion Program. Through this partnership, women receiving combined OB/SUD treatment at the XXX Program at UNMHSC will be offered expanded doula services.

1.2 Hypotheses

This is a feasibility study; therefore, the aims are to determine the feasibility of this research design in this context. Our overall hypothesis is that this study will be feasible in this population. We plan to also use this pilot data to calculate effect sizes to conduct power analyses for future research on this topic.

Aim 1. Feasibility – (a) Develop and refine participant recruitment and retention methods, (b) Develop and refine doula trauma and SUD training with input from a group

PROTOCOL TITLE: Providing Expanded Continuous Labor Support to Pregnant Women in New Mexico with Substance Use Disorders

of prior XXX Program patients (who gave birth with an SUD), (c) Estimate patient interest, satisfaction, and knowledge about doula services, (d) Estimate doula retention, satisfaction, and increased knowledge about SUD and trauma, and (e) Estimate patient attrition and follow-up rates.

Aim 2. Estimate behavioral health outcomes – (a) Traumatic birth outcome, (b) breastfeeding uptake, (c) SUD relapse and postpartum mental health change from baseline, (d) Estimate effect sizes of all theorized relationships.

2.0 Inclusion and Exclusion Criteria

How individuals will be screened for eligibility

Recruitment and screening will be by the RA or [name] at the XXX Clinic or in some cases at CASAA (e.g. if a participant hears about the study via word of mouth and calls our recruitment line, or if a participant is interested but is unable to be screened at the XXX Clinic) using a study specific screening form attached. See section 21 for more information on recruitment methods.

Inclusion/Exclusion Criteria

Inclusion Criteria: Participants must be at least 18 years old, able to participate in informed consent, able to read, write, and speak English, gestation of at least 26 weeks at baseline (necessary because of short duration of study), and plan to give birth at XXX.

Exclusion Criteria: Participants will be excluded if they are actively psychotic or are currently incarcerated. Additionally, patients identified by medical staff as unable for medical reasons to currently participate in the study will not be approached for screening. Finally, only patients who indicate they are interested in participating in a study on doula support will be screened for the study.

Special Populations

Rationale for the involvement of special vulnerable populations: We will be recruiting only pregnant women, and thus from a special vulnerable population. The justification for this is that substance relapse during pregnancy is a unique and relatively underexamined problem that is different than relapse to substance use in other populations because of (1) the high risk involved, (2) the role of pregnancy hormones in emotional dysregulation, (3) the high rates of PTSD in this population, and (4) the powerful social stigma towards substance use during pregnancy. Specially trained doulas who provide continuous labor support and postpartum follow-ups may be a pregnancy-specific intervention for these women. High risks of substance relapse among pregnant women with SUD include death from overdose, damage to the developing fetus, miscarriage, stillbirth, premature birth, involvement of child welfare, loss of parental rights, and incarceration. Additionally, pregnant women with SUD are at high risk of postpartum relapse, PTSD, and depression, resulting in a high rate of morbidity for this population. Gaining knowledge that can lead to targeted SUD treatments for pregnant women is critical to reduce the suffering and social costs resulting from prenatal substance use and postpartum problems. The risks to pregnant women and their fetuses from participation in this study are minimal, and there may be some small incidental benefits to all the women (doula and control group) and their fetuses from such

PROTOCOL TITLE: Providing Expanded Continuous Labor Support to Pregnant Women in New Mexico with Substance Use Disorders

participation (e.g. assessment reactivity could reduce their chances of relapse). Moreover, the women who are provided a doula may benefit from this added level of psychosocial support. Thus the involvement of pregnant women in this research is justified.

Additional protections for pregnant women, human fetuses and neonates are outlined under #16 below.

3.0 Study-Wide Number of Subjects

We plan to enroll 34 women in order to have a final number of 30 who complete the study.

4.0 Study Timelines

4.1 Describe:

- *The duration of an individual subject's participation in the study.*
Between 4 weeks to 20 weeks, dependent upon fetal gestational age at baseline.
- *The duration anticipated to enroll all study subjects.*
12 months from the funding date
- *The estimated date for the investigators to complete this study (complete primary analyses)*
July 1, 2020

5.0 Study Endpoints

Primary Outcomes

Relapse will be defined as percent drinking or drug use days postpartum and by drug screen at hospital admission results.

Postpartum PTSD severity – PTSD Checklist score

Postpartum depression severity – Edinburgh Postpartum Depression Scale Score

Breastfeeding Uptake

Neonatal Abstinence Syndrome

Length of NICU Stay

Secondary Outcomes

Social Support – NIH Toolbox

Labor and Delivery Autonomy

Participant Satisfaction

Doula Satisfaction

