6.0 Procedures Involved*

We will offer doula services at no cost to the 15-17 women (G1) who screen into the study and have a comparison group of 15-17 women with no doulas (TAU).

We will recruit 30-34 pregnant women (to have a final sample size of 30 women) at the XXX Program. Women in G1 will be assigned a doula. The 2nd group (G2

PROTOCOL TITLE: Providing Expanded Continuous Labor Support to Pregnant Women in New Mexico with Substance Use Disorders

Treatment as Usual) will be asked if they would potentially be interested in doula care, but will not be assigned a doula. We will conduct baseline (covariates/ dependent variables) and postpartum (outcome variables) behavioral health assessments, as well as a chart review (outcome variables and covariates).

Assessment. All questionnaires are well-validated and will be administered electronically (e.g. Qualtrics) or on paper. Baseline assessment will immediately follow screening and consent at the XXX Clinic, unless participants request more time to review the consent form or can't stay at the Clinic that day. In this case, a follow-up appointment will be made to conduct consent and/or assessments, which may then occur at the XXX Clinic or at XXX. Follow-up outcomes will be assessed at postpartum follow-ups (PPFU), ideally in the XXX Clinic, but when necessary at XXX, via the telephone, or via an online form and also by chart review. See Chart Review section below for details. Additionally, doulas will fill out a doula satisfaction survey online following each 2-week postpartum doula visit. Participants will be asked to provide a list of “locators” – people who will be able to help us find them if we lose contact before the PPFU visit. We will use a “Locator” form developed by XXX for this. This information will be stored with PII, separate from all PHI and ID numbers.

Table 1. Purpose – Measure	Baseline	2-wk PPFU
Screener – Study specific form	X	
Traumatic Life Events – Life Events Checklist - 5 ³⁸	X	X
Prenatal PTSD – PTSD Checklist - 5 ³⁹	X	X
Perinatal Depression – Edinburgh Postpartum Depression Scale ⁴⁰	X	X
Substance Use Disorders – Structured Clinical Interview for DSM5-E ⁴¹	X	
Demographics – Study specific form	X	
Current substance use – Timeline Followback ⁴²	X	X
Social Support – NIH Toolbox ⁴³	X	X
Labor & Delivery Autonomy- Mother’s Autonomy in Decision		X
Participant Satisfaction – Study specific form		X
Breastfeeding intent/uptake – Study specific form	X	X

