8.0 Data and Specimen Management

Data Analysis

Given the small scale of the pilot study, statistical analyses are intended to detect a signal rather than between-group differences. Preliminary analyses will focus on the distributional characteristics of the primary outcomes, in addition to conducting analyses for group baseline equivalency and participant attrition. Preliminary analyses will also examine group differences in demographics (e.g. age, education, gestation) at baseline. We will examine distributions using standard tests to detect outliers. For outcomes only measured at a single time point, analyses will consist of ANOVAs and Chi Square tests. For between-group contrasts ($df=1$) for measures expected to change over time (measured at baseline and PPFU) we will utilize the ANCOVA analog using multilevel modeling with outcome measures separately entered as a level 1 variable and group membership entered in level 2, with no protection for type 1 error. Meta analytic techniques⁴⁵ using mixed-model regressions will be used to determine overall impact of the intervention (all dependent variables entered into 1 distribution). The Q statistic will then be used to examine the homogeneity of the observed effect sizes associated with outcomes. Finding of heterogeneity will indicate that, on average, one or more outcomes are more sensitive to detecting treatment effects than others. Thus, we will identify those outcomes which provide the strongest signal. Given the nature of this rich dataset, many important analyses not directly tied to aims will be conducted (e.g. temporal patterns of relapse).

Power Analysis

Given the novelty of this pilot study, meaningful estimates of between group differences cannot be reasonably obtained or calculated. In fact, the objective of this study is to derive those estimates necessary for a future sufficiently powered R01 proposal.

Steps that will be taken to secure the data to maintain confidentiality

Most data will be collected electronically through a survey tool, such as Qualtrics. Some data are difficult to entirely collect this way (e.g. Timeline followback, SCID5) and will thus need to have values extracted from paper questionnaires or notes. Electronic data

PROTOCOL TITLE: Providing Expanded Continuous Labor Support to Pregnant Women in New Mexico with Substance Use Disorders

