17.0 Number of Subjects

We will recruit up to 34 participants in order to have 30 who complete the study. We plan to recruit 17 participants for each group in order to have 15 who complete the study in each group.

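### The neonatal abstinence syndrome contrast should be stratified by or adjusted for baseline opioid exposure, which is already collected and which the plan leaves out of that comparison

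*Combined protocol and SAP*

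**What the plan says.** Section 5.0 lists "Neonatal Abstinence Syndrome" among the primary outcomes, with no definition, denominator or at-risk population. Section 8.0 states: "For outcomes only measured at a single time point, analyses will consist of ANOVAs and Chi Square tests". NAS is such an outcome, and no covariate, stratum or subset is attached to it. The multilevel analogue of ANCOVA is kept for measures taken at both baseline and follow-up.

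The criteria in section 2.0 begin "Participants must be at least 18 years old, able to participate in informed consent, able to read, write, and speak English" and go on to gestation and place of birth; no substance is specified. Section 1.1 describes women in care for substance use disorders generally. The relapse endpoint in section 5.0 spans alcohol and drugs: "Relapse will be defined as percent drinking or drug use days postpartum".

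The exposure data are in hand. Table 1 in section 6.0 schedules "Substance Use Disorders – Structured Clinical Interview for DSM5-E" and the Timeline Followback at baseline. The chart review in section 20.0 reaches back to the first prenatal clinic visit, and section 6.0 expects it to supply covariates as well as outcomes. Section 8.0 plans a check of baseline equivalence, but its examples are demographic. Section 6.0 says that one group receives a doula; it does not say how women are allocated, or whether substance plays a part.

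**The concern.** NAS is a withdrawal outcome. If an infant can develop it only after relevant prenatal exposure, taken here to be mainly opioids, used or prescribed (an assumption, since the documents do not say), then the number of cases in each group depends heavily on how many exposed women are in that group. Exposure at or before baseline precedes any doula contact, so it is a prognostic factor and not a result of the intervention.

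With about 15 women per group, an unadjusted comparison carries all the variation in exposure mix into the NAS estimate. Section 8.0 says that the study exists to produce estimates for a larger trial, and it plans to pool the outcomes and identify those with the strongest signal. A NAS effect size less precise than the data allow would feed both uses.

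**Working it through.** **The plan's own figures.** Section 17.0: "We plan to recruit 17 participants for each group in order to have 15 who complete the study in each group". So 2 × 17 = 34 enrolled and 2 × 15 = 30 completing, which agrees with section 3.0. The plan states no NAS rate, effect size or power, so there is no further figure to reproduce.

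**Assumptions (not in the documents).** Exposed share q = 0.5 to 0.9. NAS risk in exposed infants a = 0.5 to 0.7, and 0 in the others. No doula effect. Group size n = 15. Overall NAS risk p = qa.

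**1. NAS variance explained by exposure.** R² = a²q(1−q) / [p(1−p)].

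**2. Chance imbalance.** The numbers exposed are two independent Binomial(15, q) counts. The probability that they differ by 3 or more is 36% at q = 0.5, 32% at 0.7, 25% at 0.8 and 12% at 0.9.

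**3. Effect of a gap of exactly 3.** The expected shift in the risk difference is (3/15) × a, which is 0.10 at a = 0.5 and 0.14 at a = 0.7.

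**4. Standard errors of the risk difference.** All infants, unadjusted: √[2p(1−p)/15]. Restricted to exposed infants, approximately: √[2a(1−a)/(15q)].

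| q | a | p | R² | SE, all infants | SE, restricted |
|---|---|---|---|---|---|
| 0.5 | 0.5 | 0.25 | 0.33 | 0.16 | 0.26 |
| 0.5 | 0.7 | 0.35 | 0.54 | 0.17 | 0.24 |
| 0.9 | 0.5 | 0.45 | 0.09 | 0.18 | 0.19 |
| 0.9 | 0.7 | 0.63 | 0.19 | 0.18 | 0.18 |

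**5. Gain from adjustment.** In large samples the SE falls by 1 − √(1−R²): 5% at R² = 0.09 and 32% at R² = 0.54. Simulation with 15 per group gives roughly 2% to 31%, with the lower end at q = 0.9, a = 0.5, where it may be slightly under 2%. Adjustment gains less than the formula there because groups this small make the exposure effect costly to estimate.

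**6. Type I error of the unadjusted chi-square** (two-sided 0.05, by exact enumeration, a = 0.5 to 0.7). Averaged over all imbalances at q = 0.7, it rejects 4.6% to 5.2% of the time. Given 10 exposed women in each group it rejects 0.7% to 2.7% of the time; given 8 against 12, about 9%. The error is near nominal on average but depends on the exposure split obtained.

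**The case against.** The strongest objection is that the size rests on a fact the documents do not supply. Women come from one clinical program whose substance mix is not stated. A relapse measure that counts drinking does not show that women without opioid exposure will enrol. If all are exposed, the problem vanishes. This stands, and it is why every figure above is conditional.

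Four stronger readings are tempting and are not supported:

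- *The plan fixes an all-infant denominator.* It gives no denominator. All infants is only the default reading of a chi-square with no subset named. Nor does the plan rule out using its covariates; it just does not tie them to NAS.
- *Chance imbalance passes for a doula effect.* Under random assignment, chance imbalance is already part of the sampling error, and step 6 shows the average type I error near 5%. A 10 to 14 point shift is about 0.55 to 0.80 of one unadjusted SE. Because the plan does not describe random assignment, a systematic difference in exposure is possible. That would be an allocation problem affecting every outcome and is wider than this point.
- *Unexposed infants dilute the effect.* This holds for the risk difference, which is multiplied by q. The risk ratio is unchanged when unexposed infants have zero risk.
- *Restricting to exposed infants is the natural cure and loses no events.* Step 4 shows that restriction leaves the SE of the risk difference unchanged at best and raises it from 0.16 to 0.26 at worst. The target difference also grows, but in an illustration with NAS risks of 0.6 and 0.3 in exposed infants, power rises only from 17% to 22% at q = 0.5 and from 32% to 36% at q = 0.9. Restriction by baseline exposure can also omit infants first exposed later or affected by other substances.

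It is also fair to say that this is a feasibility pilot looking for a signal. But NAS is listed as primary and its effect size is meant for reuse, so a low-cost gain in precision is worth taking.

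**Conclusion.** The point holds as a matter of precision. A strong baseline predictor of a primary outcome is collected but given no role in that outcome's comparison. For a mixed cohort, under the stated assumptions, exposure explains about 9% to 54% of NAS variance, and using it lowers the SE of the risk difference by roughly 2% to 31%. The gain is largest when about half the women are exposed and small when nearly all are. The conclusion depends on an exposed share and NAS risks that the documents do not give, and on little or no NAS risk in infants without opioid exposure. It does not depend on any claim that the planned test has the wrong overall error rate.

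**What to change.** Add to section 8.0: the NAS contrast is made over all infants, stratified by or adjusted for maternal opioid exposure recorded at or before baseline (structured clinical interview, Timeline Followback, and prenatal chart including prescribed treatment), as a risk difference with 95% CI; the number exposed is reported per group. Use only exposure up to baseline, because later use may be affected by the doula. Name the interval method in advance, since the unexposed stratum may contain no events.

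Give the contrast among infants of baseline-exposed women as a supporting analysis. State its denominator per group, that its interval is generally wider, and that it may miss infants first exposed after baseline or affected by other substances.

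The cost is a sentence or two and one derived variable from data already collected. No visit, measure or participant is added. If every woman proves to be opioid-exposed, the all-infant and restricted analyses coincide and nothing is lost.

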6.0 Procedures Involved*

We will offer doula services at no cost to the 15-17 women (G1) who screen into the study and have a comparison group of 15-17 women with no doulas (TAU).

We will recruit 30-34 pregnant women (to have a final sample size of 30 women) at the XXX Program. Women in G1 will be assigned a doula. The 2nd group (G2

PROTOCOL TITLE: Providing Expanded Continuous Labor Support to Pregnant Women in New Mexico with Substance Use Disorders

Treatment as Usual) will be asked if they would potentially be interested in doula care, but will not be assigned a doula. We will conduct baseline (covariates/ dependent variables) and postpartum (outcome variables) behavioral health assessments, as well as a chart review (outcome variables and covariates).

Assessment. All questionnaires are well-validated and will be administered electronically (e.g. Qualtrics) or on paper. Baseline assessment will immediately follow screening and consent at the XXX Clinic, unless participants request more time to review the consent form or can't stay at the Clinic that day. In this case, a follow-up appointment will be made to conduct consent and/or assessments, which may then occur at the XXX Clinic or at XXX. Follow-up outcomes will be assessed at postpartum follow-ups (PPFU), ideally in the XXX Clinic, but when necessary at XXX, via the telephone, or via an online form and also by chart review. See Chart Review section below for details. Additionally, doulas will fill out a doula satisfaction survey online following each 2-week postpartum doula visit. Participants will be asked to provide a list of “locators” – people who will be able to help us find them if we lose contact before the PPFU visit. We will use a “Locator” form developed by XXX for this. This information will be stored with PII, separate from all PHI and ID numbers.

Table 1. Purpose – Measure	Baseline	2-wk PPFU
Screener – Study specific form	X	
Traumatic Life Events – Life Events Checklist - 5 ³⁸	X	X
Prenatal PTSD – PTSD Checklist - 5 ³⁹	X	X
Perinatal Depression – Edinburgh Postpartum Depression Scale ⁴⁰	X	X
Substance Use Disorders – Structured Clinical Interview for DSM5-E ⁴¹	X	
Demographics – Study specific form	X	
Current substance use – Timeline Followback ⁴²	X	X
Social Support – NIH Toolbox ⁴³	X	X
Labor & Delivery Autonomy- Mother’s Autonomy in Decision		X
Participant Satisfaction – Study specific form		X
Breastfeeding intent/uptake – Study specific form	X	X

Psychosocial Intervention. There will be 3 Doula visits: 1) a prenatal visit at home/clinic, 2) continuous labor support, and 3) a 2-week postpartum follow-up visit at home/clinic. Continuous labor support will occur at the hospital, but may begin at the XXX clinic or homes.

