9.0 Withdrawal of Subjects

All participants will be informed of the right to withdraw from the study at any time and still receive full compensation for their time. Participants can withdraw from the study at any time and withdraw their consent for us to use their PHI at any time, by notifying us in writing. Participants have been notified in the consent document that the research team will not be required to destroy or retrieve any of their or their baby's health information that has already been used or shared before their withdrawal is received. Participants will be withdrawn from the study if it becomes apparent that their participation in the study is endangering their safety or if they are found to no longer meet eligibility criteria. Failure to complete the baseline assessments may also result in withdrawal from the study.

However, failure to complete follow-up assessments or changing their mind about having a doula will not be cause for withdrawal, but will be tracked as a feasibility outcome in the study file. Participants who leave the XXX program, but who do not withdraw from the study will still be contacted to complete a final assessment, so that we can evaluate factors involved in this outcome as part of feasibility testing. Participants have given us contact information at baseline and agreed that we can contact them for follow-up assessments. This is also in the consent form. (See locator form and consent form.)

Unless participants withdraw consent at the time of being withdrawn from the study, their data may still be used in analyses. Data from participants who have withdrawn consent will be destroyed if it has not already been used.

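### Doula satisfaction is surveyed only after the 2-week postpartum doula visit, so pairings without that visit are not surveyed and the Aim 1(d) estimate is at risk of bias, probably upward

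*Combined protocol and SAP*

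**What the plan says.** Section 1.2 lists among the Aim 1 feasibility items "d) Estimate doula retention, satisfaction, and increased knowledge about SUD and trauma". Section 5.0 lists "Doula Satisfaction" as a secondary outcome and gives no scale, unit of analysis or summary measure.

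The only data collection rule for this outcome is in section 6.0: "doulas will fill out a doula satisfaction survey online following each 2-week postpartum doula visit". The same section describes three doula contacts: a prenatal visit, labor support, and "3) a 2-week postpartum follow-up visit at home/clinic". The survey is thus attached to the last of the three. Table 1 has rows for participant measures only and none for doulas.

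Section 9.0 foresees pairings that do not run their course. For the woman, "changing their mind about having a doula will not be cause for withdrawal, but will be tracked as a feasibility outcome". Women who leave the program and "who do not withdraw from the study will still be contacted to complete a final assessment". Neither sentence has a counterpart for the doula. Section 8.0 plans an analysis of participant attrition and does not mention missing doula surveys.

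**The concern.** Tying a satisfaction survey to completion of the service selects on the outcome that a feasibility study wants to learn about. If a woman declines her doula, cannot be reached after birth, or loses her doula because the doula quits, there may be no third visit and so no survey. Doulas may well be less satisfied with such pairings than with those that reach the end.

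At stake is one part of Aim 1: whether the work is acceptable to the doulas. A figure drawn from completed pairings alone could make the service look easier to staff than it is. No analysis could correct this afterwards, because the responses would not exist.

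**Working it through.** **1. Which pairings produce a survey under the rule as written**

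| What happens to the pairing | 2-week doula visit? | Survey? |
|---|---|---|
| All three contacts take place | Yes | Yes |
| Doula misses the birth but makes the postpartum visit | Yes | Yes |
| Woman leaves the program but stays in the study | Possible (the visit may be at home) | Only if the visit occurs |
| Woman changes her mind about the doula before the visit | No | No |
| Woman cannot be reached by the doula after birth | No | No |
| Doula quits before the visit | Not by that doula | None from that doula for that pairing |
| Woman gives her postpartum assessment by telephone or online form, without a doula visit | No | No |

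The last row matters for counting. Section 6.0 allows the woman's own assessment to be done remotely, while sections 6.0 and 15.0 place the doula visit at home, clinic or hospital. A woman can therefore complete the study although her pairing has no doula survey.

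**2. The plan's own figure**

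The plan states no figure for doula satisfaction or for the share of pairings surveyed. The nearest is in section 17.0: "We plan to recruit 17 participants for each group in order to have 15 who complete the study in each group". The implied loss is 2/17 = 11.8%, and 15/(1 − 2/17) = 17. This only restates the plan's numbers, because no attrition rate is given separately. It concerns women completing the study, not doula visits, so it is a reference point and not an estimate of missed visits.

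**3. Size of the possible bias**

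Let f be the share of assigned pairings with no 2-week visit, p_s the proportion satisfactory among surveyed pairings, and p_u the proportion among the rest.

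- Value over all pairings = (1 − f) × p_s + f × p_u
- Value the plan would report = p_s
- Bias = f × (p_s − p_u)

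Inputs: 17 pairings, taking each woman in the doula group as one pairing (section 17.0). The number unsurveyed, p_s and p_u are all assumed. I use 2 unsurveyed (f = 0.118, matching the 17-to-15 allowance) and 4 unsurveyed (f = 0.235, since missed visits can exceed study drop-out).

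| Unsurveyed | p_s | p_u | All pairings | Bias (points) |
|---|---|---|---|---|
| 2 of 17 | 90% | 90% | 90.0% | 0 |
| 2 of 17 | 90% | 60% | 86.5% | +3.5 |
| 2 of 17 | 90% | 30% | 82.9% | +7.1 |
| 4 of 17 | 90% | 60% | 82.9% | +7.1 |
| 4 of 17 | 90% | 30% | 75.9% | +14.1 |
| 2 of 17 | 80% | 100% | 82.4% | −2.4 |
| 4 of 17 | 80% | 100% | 84.7% | −4.7 |

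Example: 4/17 × (0.90 − 0.30) = 0.235 × 0.60 = 0.141.

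The arithmetic ceiling, 100% against 0%, equals f itself: 11.8 points with 2 unsurveyed and 23.5 points with 4.

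**4. Effect of surveying every pairing**

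If all 17 pairings are surveyed and all surveys are returned, f = 0 and this bias is 0. If 4 pairings lack the visit and 2 of those 4 are answered, the share still missing falls from 4/17 to 2/17.

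**The case against.** The strongest reply is that this is a small matter. Doula satisfaction is the last of the listed secondary outcomes and one element of a five-part Aim 1. Breakdown of pairings is partly visible elsewhere: changes of mind are tracked under section 9.0, and Aim 1(e) estimates attrition. A pairing that ended before the doula met the woman may offer little to rate. These points limit the weight of the concern. They do not supply the doula's view of a pairing that failed, which is the missing information.

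A reader might also infer more than the documents support:

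- **That the estimate is biased upward.** The documents have no data on satisfaction in broken pairings. A visit missed because of relocation or lost contact need not reflect the doula's experience, and the table above shows zero and negative bias under other assumptions. Upward is the plausible direction, not a demonstrated one.
- **That every troubled pairing is excluded.** A doula who missed the birth but made the postpartum visit is surveyed. A woman leaving the program does not by itself prevent the visit.
- **That some doulas are never surveyed.** The rule works per visit, and neither the number of doulas nor the pairings per doula is stated. A doula with several clients may be surveyed about another one. The gap is at the level of the pairing.
- **That the doula retention estimate is distorted.** Retention is a separate item in Aim 1(d) and does not depend on when this survey is sent.
- **That the plan would report 100% where the truth is 13/17 (76%).** This takes 4 missing pairings and the most extreme contrast possible. It is a ceiling, not an expectation.

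**Conclusion.** The concern holds in a limited form. As written, the Aim 1(d) satisfaction estimate describes only pairings with a completed 2-week visit. It carries a risk of selection bias, probably upward, that cannot be repaired once the study is over. Under the middle assumptions shown, the overstatement is 3.5 to 7.1 points with 2 of 17 pairings unsurveyed and 7.1 to 14.1 points with 4. These sizes rest on assumed satisfaction levels and an assumed number of missed visits, and the documents fix neither. That the direction is uncertain does not count against acting, since without the missing surveys nobody could tell whether a bias exists. The point is worth correcting because satisfaction is a named feasibility item and the correction is cheap. The documents do not say that this outcome decides whether a later trial goes ahead.

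**What to change.** 1. Keep the survey after the 2-week visit as it is.
2. Send the same online survey when a pairing ends early, when the doula's participation ends, or when the 2-week visit has not taken place by a cut-off date. The plan gives no window for that visit, so the sponsor would need to state one for this purpose.
3. Record for each assigned pairing which of the three contacts took place.
4. Report satisfaction over all assigned pairings, state how many were surveyed out of how many assigned, and show results by contacts completed. Keep a pairing that ended before the two met in the assigned count, marked as having nothing to rate.

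A single trigger set at 2 weeks after birth or the end of the pairing, whichever is first, would be a poor substitute. Where the third visit falls after day 14, it would survey an ordinary pairing before that visit and so change what is being rated.

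The cost is a few extra requests on an existing form, for a group of at most 17 pairings. Some doulas who have left may not reply, so the gap may shrink rather than close.
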